Duration of Exposure	
Phase I (Randomized, Blinded): For subjects randomized to the active treatment, stimulation will occur at a maximum of 120% magnetic field intensity relative to the subject's resting motor threshold (MT), at 10 pulses per second (10 Hz) for 4 seconds, with an intertrain interval of 26 seconds. During the treatment, intensity can be reduced, as needed, to 80% for tolerability. Upward titration with goal of return to maximum intensity (not to exceed 120% MT) will occur as tolerated by each participant. This is not expected to impact treatment response but may make the treatment experience more comfortable for the participating adolescents. Treatment sessions will last for 37.5 minutes (75 trains) to provide a total of 3,000 pulses per treatment session. A total of 30 treatments will be completed within 6-8 weeks of Phase I treatment initiation.
 
Phase II (Non-Randomized, Open-label): Acute Treatment (Arm 1): Subjects who did not achieve adequate clinical response to treatment in Phase I will be offered the opportunity to undergo acute rTMS treatment using the known-active therapy coil in Phase II. The treatment schedule and parameters will be identical to that in Phase I; i.e. daily stimulation will occur at a maximum of 120% magnetic field intensity relative to the subject's resting motor threshold (MT), at 10 pulses per second (10 Hz) for 4 seconds, with an intertrain interval of 26 seconds. During the treatment, intensity can be reduced, as needed, to 80% for tolerability. Upward titration with goal of return to maximum intensity (not to exceed 120% MT) will occur as tolerated by each participant. Treatment sessions will last for 37.5 minutes (75 trains) to provide a total of 3,000 pulses per treatment session. A total of 30 treatments will be completed within 6-8 weeks of Phase II treatment initiation.
 
Therefore, subjects who had been randomized to active treatment during Phase I and subsequently enroll in the Acute Treatment (Arm 1) of Phase II will receive a total of 60 active treatments using stated study parameters within the 12- to 16-week combined timeframes.
 
Subjects who were randomized to sham treatment during Phase I and subsequently enroll in the Acute Treatment (Arm 1) of Phase II will receive a total of 30 active treatments using stated study parameters within the 12- to 16-week combined timeframes.
 
Maintenance Treatment (Arm 2): Subjects who achieve adequate clinical response to treatment in Phase I will be offered the opportunity to undergo maintenance rTMS treatment using the known-active therapy coil in Phase II. Subjects will receive one treatment every other week for 52 weeks for a total of 26 treatments. Stimulation will occur at a maximum of 120% magnetic field intensity relative to the subject's resting motor threshold (MT), at 10 pulses per second (10 Hz) for 4 seconds, with an intertrain interval of 26 seconds. During the treatment, intensity can be reduced, as needed, to 80% for tolerability. Upward titration with goal of return to maximum intensity (not to exceed 120% MT) will occur as tolerated by each participant. Treatment sessions will last for 37.5 minutes (75 trains) to provide a total of 3,000 pulses per treatment session.
 
Combined duration of exposure for Phase I active/Phase II maintenance subjects would be 56 active treatments over 58 to 60 weeks. Combined duration of exposure for Phase I sham/Phase II maintenance subjects would be 26 active treatments over 58 to 60 weeks.

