----------------------	---

Reference Therapy	Subjects in Phase I who are randomized to sham treatments will have schedules, systematic assessments, and treatment approaches that are identical to subjects randomized to active treatments. Subjects, treaters, and clinical raters will not know whether the treatment is active or sham in nature (double-blinded). The sham coil is identical in its appearance to the active coil. Furthermore, Neuronetics, Inc. has created an acoustic matching profile that renders the sensory experience of the treatments virtually indistinguishable to subjects or researchers. The acoustic signal creates a painless percussive sensation that will be felt by the subject and will assist in simulating the active condition.
Concomitant Therapy	
Permitted: Subjects are expected to be on stable dose pharmacotherapy with one of the antidepressants listed in protocol Section 4.1 (Inclusion Criteria). Any other medication change including initiation, discontinuation, or dose adjustment of medication, needs to be discussed with the site PI and approved before implementation.
 
Prohibited: Initiation of medication listed in protocol Section 4.2 (Exclusion Criteria) is not permitted during either phase of the study. Dose adjustment or initiation of permitted medications (Section 4.1 Inclusion Criteria) after enrollment must be approved by the site PI prior to implementation.

Statistical Methodology	
Statistical analysis plan for objectives 1, 2a, 2b : Treatment outcomes defined as remission, response, or nonresponse will be assessed using a logistic regression model with independent variables of treatment number (i.e. #10 vs. #20 vs. #30) and gender (male vs. female) will be analyzed at the 0.05 significance level. The primary outcome measures will include the CDRS-R and CGI-I.
 
Statistical analysis plan for objective 3 (data from MCR site only): The hypotheses will be tested using t-tests. Additionally, analyses of covariance will be performed to control for potentially important covariates or confounders, such as age or gender. Non-parametric distribution will be analyzed by non-ANOVA statistics.

1 Introduction

This document is a protocol for a human research study. This study will be carried out in accordance with the procedures described in this protocol, applicable United States government regulations, Mayo Clinic of Rochester (MCR), and the Medical University of South Carolina (MUSC) policies and procedures.

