4.4 Early Withdrawal of Subjects

4.4.1 When and How to Withdraw Subjects

Subjects will be withdrawn from the study immediately if a seizure, DSM-IV-confirmed treatment-induced mania, or other UADE occurs. Subjects will also be withdrawn from the study, at the time of notification of study staff, if at any point they meet any of the exclusionary criteria outlined in protocol Section 4.2.

Subjects enrolled in Maintenance Treatment (Arm 2) in Phase II will be withdrawn from the study if they experience a worsening of their depression. Worsening of depression will be defined as a CDRS-R score increase of >33% of Phase II baseline or a raw CDRS-R score of ≥ 40 , whichever occurs first, accompanied by clinician determination of significant

clinical deterioration as noted by a clinical global improvement (CGI-I) scale score of ≥ 6 (much worse or very much worse). Worsening of suicidal ideation and behavior will be defined as an increase of the Columbia – Suicide Severity Rating Scale (C-SSRS) suicidal ideation score of ≥ 4 or suicidal behavior including actual suicide attempts, interrupted/aborted attempts, or preparatory acts or behavior. These subjects will be referred to the care of their primary clinician or psychiatric provider. Subjects and families will be given recommendations for alternative treatment options and will be offered care through the clinic. There are no funds to pay for psychiatric hospitalization of a subject in this study; however, research staff and physicians will be available at all times to evaluate subjects with adverse behavioral consequences and, if necessary, arrange for admission to a local hospital.

Subjects may decide to withdraw from the study at any time, for any reason, including inability to tolerate study treatment, lack of improvement of depressive symptoms, or worsening of depressive symptoms. There are no currently-known risks associated with abrupt discontinuation of treatment with rTMS.

Subjects will be encouraged to remain compliant with all prescribed medications and expected study visits. Nonadherence to expected study visits and/or medications will be documented and may result in removal from the study. This will be clearly discussed during the consent/assent process and reinforced throughout the study through regular screening for changes in medications or issues with compliance.

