5.4 Subject Compliance Monitoring

During Phase I of the trial, subjects will complete 30 treatments within a 6- to 8-week timeframe. This schedule allows for the missing and/or rescheduling of up to 10 treatments over this timeframe. Subjects who are unable to comply with this schedule may be withdrawn from the investigational treatment portion of the study but will be offered ongoing mood, cognitive, safety, and imaging assessments as outlined in the study timeline (Table 4).

During Phase II of the trial, the Non-Responder Cohort from Phase I will receive acute rTMS treatment according to the schedule in Phase I. They will likewise be expected to complete 30 treatments within 6 to 8 weeks (Table 5).

The Responder Cohort from Phase I will receive maintenance treatments in Phase II with a biweekly treatment schedule over the course of 52 weeks (26 treatments). A total of 8 sessions can be missed over the course of 52 weeks (Table 6). More than 8 missed sessions will result in subject withdrawal from the study.

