7.2 Statistical Methods

Descriptive Statistics

Univariate descriptive statistics and frequency distributions will be calculated as appropriate for all variables. Baseline values for demographic, clinical, and outcome variables (primary and secondary) will be tabulated for the treatment groups. These analyses will help identify potential confounding variables to be used as covariates in sensitivity analyses. Distributions across subgroups used in randomization will be compared to assess whether the randomization was successful in equalizing distributions of these prognostic variables across treatment groups.

Statistically significant differences on overall comparisons will be explored using multiple pairwise comparisons of each of the (treatment) groups using Bonferroni correction for multiple comparisons. Mean scores and standard deviation for each group will be calculated.

Subsequent multiple comparisons via Tukey's procedure will be set at 0.01 to control Type I error rate.

Primary Hypotheses:

- 1) Adolescents in Phase I treated with active rTMS at the left dorsolateral prefrontal cortex (L-DLPFC) will have significant mood improvement when compared to sham treatment.
- 2) Adolescents in Phase II treated with maintenance rTMS at the L-DLPFC will achieve sustained response of the depressive symptoms.

Phase II represents a proof of concept/preliminary study of long-term maintenance for treatment responders (either active or sham in Phase I) and an opportunity for open-active treatment in nonresponders. The inclusion of phase II is ethically necessary to ensure that all pediatric participants are offered an opportunity to receive active treatment if unresponsive in phase I. The analysis of data collected as part of phase II is exploratory and will include primarily descriptive statistics.

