Treatment outcomes for both phases will be defined as response (CDRS-R raw score <28 & CGI-I ≤2 & CGI-S ≤2), or nonresponse (CDRS-R raw score ≥28 and CGI-I ≥3) assessed using a logistic regression model with independent variables of treatment number (i.e. #10 vs. #20 vs. #30) and gender (male vs. female) will be analyzed. Assessing potential gender effects will be a secondary analysis. The primary analysis will not adjust for gender. Although we anticipate that more females than males will participate in the study, we assume that the distribution of gender will be similar between treatment arms and have no a priori reason to suspect that the efficacy of treatment will be gender specific.

Serious adverse events will be reported as noted within the application. All adverse events will be summarized according to treatment groups. Given the sample size for the current study, the statistical power for detecting differences between groups is limited. However, we will compare between groups using an exact test.

All statistical tests will be performed at the 0.05 significance level.

Secondary Hypotheses (for MCR site only):

Baseline glutamate, reported as a CSF-corrected absolute concentration and as an overlapping resonance with glutamine, will be significantly higher in both AC and L-DLPFC in depressed adolescents as measured by ^1H -MRS at 3T when compared to data derived from previously scanned healthy controls.

In comparison to non-remission subjects, depressed adolescents treated with rTMS who achieve remission (defined as a CDRS-R raw score <28 and CGI-I ≤ 2 and CGI-S ≤ 2 at treatment completion) will exhibit a greater decrease in glutamine, reported as a CSF-corrected absolute concentration percent change (baseline to endpoint) in AC and L-DLPFC as measured by ^1H -MRS at 3T.

The hypotheses will be tested using t-tests. Additionally, analyses of covariance will be performed to control for potentially important covariates or confounders, such as age or gender. Non-parametric distribution will be analyzed by non-ANOVA statistics.

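### The only model named for sustained response in Arm 2 uses treatments #10, #20 and #30, but Arm 2 has 26 treatments, and the plan does not say how Arm 2 withdrawals count

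*Combined protocol and SAP*

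**What the plan says.** Section 7.2 gives, as the second entry under its primary hypotheses: "Adolescents in Phase II treated with maintenance rTMS at the L-DLPFC will achieve sustained response of the depressive symptoms". Section 2.1.3 likewise makes sustained benefit over 26 maintenance sessions the primary objective of Arm 2. The paragraph after the hypotheses in 7.2 qualifies this: "The analysis of data collected as part of phase II is exploratory and will include primarily descriptive statistics".

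Section 7.2 then sets one outcome for the whole trial: "Treatment outcomes for both phases will be defined as response (CDRS-R raw score <28 & CGI-I ≤2 & CGI-S ≤2", with nonresponse as the other category. It is analysed by logistic regression with "independent variables of treatment number (i.e. #10 vs. #20 vs. #30) and gender (male vs. female) will be analyzed". The Statistical Methodology entry of the Study Summary describes the same model under the label "Statistical analysis plan for objectives 1, 2a, 2b"; objective 2b is maintenance treatment in Phase I responders, that is, Arm 2.

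On the Arm 2 schedule, the Study Summary says: "Subjects will receive one treatment every other week for 52 weeks for a total of 26 treatments". Section 5.4 agrees ("biweekly treatment schedule over the course of 52 weeks (26 treatments"), allows 8 missed sessions, and withdraws subjects who miss more. Section 3.2.3 and Table 6 have the mood scales rated monthly, and 6.3.2.2 adds a visit after treatment 26.

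Section 4.4.1 states: "Subjects enrolled in Maintenance Treatment (Arm 2) in Phase II will be withdrawn from the study if they experience a worsening of their depression". The criterion is a CDRS-R rise of more than 33% over Phase II baseline, or a raw score of 40 or more, together with CGI-I of 6 or more. Table 6, footnote e, has ratings taken at withdrawal.

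**The concern.** Treatments 10, 20 and 30 are the assessment points of the 30-session acute course used in Phase I and Arm 1. Carried into Arm 2, one of the three does not exist and the other two are arbitrary points within a year of maintenance. Response status at two isolated treatment numbers also says nothing about whether response was held between them or up to the end.

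The plan gives no definition, time point or denominator for the word sustained. Subjects leave Arm 2 because they worsen or because they miss sessions, and nothing says how either exit counts.

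Durability is the main result that Arm 2 can offer. Without a definition fixed in advance, the reported figure depends on choices made after the data are seen, chiefly whether those who left stay in the denominator.

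**Working it through.** **Treatment count.** One treatment every 2 weeks for 52 weeks (Study Summary): 52 / 2 = 26. The stated figure reproduces.

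**Where the model's time points fall in Arm 2.** Taking treatment k as falling near week 2k:

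| Treatment | Approximate week | In Arm 2? |
|---|---|---|
| #10 | 20 | yes |
| #20 | 40 | yes, if reached |
| #26 | 52 | yes, but not in the model |
| #30 | 60 | no, beyond the 52-week course |

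**Can a compliant subject miss #20?** Section 5.4 tolerates 8 missed sessions. If they are not made up, 26 − 8 = 18 treatments are delivered. Such a subject stays in the study and never reaches #20.

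**The same misfit in 7.3.** The Completer Cohort requires 30 sessions. Applied to Arm 2, nobody could be a completer. A subject who attended all 26 sessions would meet the Partially Adherent definition (at least 20, fewer than 30).

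**Likely size of Arm 2.** Section 7.1 assumes response in 65% on active and 25% on sham, and the Study Summary allocates 38 and 37. Then 38 × 0.65 + 37 × 0.25 = 24.70 + 9.25 = 33.95, or about 34 eligible if every responder accepts. Uptake is not stated; if half accept, 17.

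**How much the handling of withdrawals matters.** Let N be entrants, w withdrawals, and assume that every retained subject is still in response. Scoring retained subjects only gives (N − w)/(N − w). Scoring all entrants, with withdrawal counted as loss of response, gives (N − w)/N. With N = 34 and assumed values of w:

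| Withdrawn | Retained only | All entrants |
|---|---|---|
| 5 | 29/29 = 100% | 29/34 = 85.3% |
| 10 | 24/24 = 100% | 24/34 = 70.6% (exact 95% CI 52.5% to 84.9%) |
| 15 | 19/19 = 100% | 19/34 = 55.9% |

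This illustration does not separate worsening from missed sessions; all withdrawals count as loss of response.

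**Does the rating at withdrawal settle the status?** Withdrawal for worsening of depression needs CGI-I of 6 or more, so the subject fails the CGI-I ≤2 part of the response definition and is never a responder at that point. The two categories in 7.2 are not exhaustive, however. For an assumed entry CDRS-R of 17 to 20, the >33% limb is first met at 23 to 27. Nonresponse in 7.2 requires CDRS-R of 28 or more as well as CGI-I of 3 or more, so that subject is in neither category. For entry scores of 21 to 27, the limb is first met at 28 to 36.

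**The two limbs in 4.4.1.** Arm 2 entry requires CDRS-R below 28 (3.1 and 6.3). The highest whole-number entry score is 27, and 27 × 1.33 = 35.91, so a score of 36 exceeds +33% for every permitted entry score. The limb at 40 or more can never be the first to act.

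**The case against.** The strongest reply is that Phase II is declared a preliminary, exploratory study with mainly descriptive analysis. A reader might infer from the word primary that a confirmatory test fails here. The documents do not support that: no power, success threshold or control group is attached to hypothesis 2. What stands against the plan is narrower. The primary label was kept, an acute-course model was assigned to Arm 2 in two places, and even a descriptive rate needs a definition, a time point and a denominator.

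A reader might also infer that the trial cannot show sustained response, or that its durability figure will be inflated. Neither follows. No section restricts Arm 2 to subjects still in treatment. Section 7.3 defines the intention-to-treat population as everyone who started a session, and 7.1 names last observation carried forward for the primary analysis, although neither is said to govern Arm 2. Ratings are taken at withdrawal, and 4.4.2 offers continued assessment to those who choose to stop treatment. Since worsening of depression requires CGI-I of 6 or more, carrying that rating forward would not create a false responder. Overstatement arises only under an observed-only rule that the plan neither adopts nor excludes. Missed-session withdrawals are less protected: carrying forward could leave such a subject classed as a responder.

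Nor does the plan omit the monthly ratings or the end-of-course visit. Section 3.2.3 makes the monthly scales the Arm 2 primary outcome measures, and 6.3.2.2 schedules the visit after treatment 26. They are absent from the model's time points, not from the trial.

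**Conclusion.** The point holds as a mismatch between a stated analysis and its arm. The model assigned to objective 2b has a time point that cannot occur, a second that a compliant subject may not reach, and none at the end of maintenance, so it does not capture sustained response. The data that could capture it are already scheduled. This does not touch the Phase I comparison, and no Phase II inference is lost, because none was planned beyond description.

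The size of any distortion depends on a rule that the plan leaves open. If retained subjects alone were scored, the excess would be about 15, 29 or 44 percentage points for 5, 10 or 15 withdrawals among 34 entrants. Those withdrawal counts are assumptions, as are full uptake and complete response among those retained. If all entrants were kept and worsening counted as loss of response, that source of overstatement would disappear.

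The redundant limb in 4.4.1 is arithmetically clear, but it is a separate inconsistency in a withdrawal rule. It does not determine how response is scored: a subject at 28 or above already fails the CDRS-R part of the response definition at a monthly rating.

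**What to change.** In 7.2 and the Study Summary:

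- Limit the #10/#20/#30 model to Phase I and Arm 1.
- Label hypothesis 2 exploratory, in line with the paragraph that follows it.
- Define sustained response for Arm 2 on the monthly ratings through the post-treatment-26 visit. Two workable forms are response criteria met at every monthly rating, or time to first loss of response. Either would do for an arm of this size; what matters is choosing one in advance.
- Use all Arm 2 entrants as the denominator.
- Count withdrawal for worsening as loss of response. State how missed-session withdrawals are handled (for example, censored in a time-to-event summary), with a sensitivity analysis that treats them the other way.
- State which response definition applies at the monthly ratings. Entry to Arm 2 (3.1 and 6.3) has no CGI-S condition, whereas 7.2 requires CGI-S ≤2, so a subject can enter without being a responder under 7.2.

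Separately, the >33% and ≥40 limbs in 4.4.1 and the <28 entry criterion must be reconciled by the sponsor.

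The cost of the analysis changes is slightly more analysis text and possibly a lower reported durability figure. They need no new visits, ratings or subjects.

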2.2 Secondary Objective (MCR site only)

Secondary objectives of this study are to evaluate, by proton magnetic resonance spectroscopy (¹H-MRS) at 3 Tesla (3T), the following neurometabolic biomarkers:

- 1) Define regional specificity [anterior cingulate (AC) and left dorsolateral prefrontal cortex (L-DLPFC)] of cerebral metabolites (i.e. glutamate and glutamine) in adolescent depression.
- 2) Study whether specific neurochemical resonances are associated with response or remission of clinical depressive symptoms when rTMS is used to treat adolescent depression.

To accomplish these goals, the MCR site will utilize ¹H-MRS, a valuable, non-invasive method to study in-vivo brain biochemistry. Of the available imaging paradigms, ¹H-MRS is uniquely suited to investigate biochemical mechanisms of treatment action that are objectively

measurable and clinically relevant. As there is increasing interest in glutamatergic dysregulation in mood disorders, this project will utilize ^1H -MRS at 3T to study specific neurometabolic levels in the primary brain regions associated with major depressive disorder [anterior cingulate (Brodmann's areas 24a/b and 32) and L-DLPFC (Brodmann's 9/46)]. The goal of this aspect of the proposal is to evaluate whether anterior cingulate and prefrontal cortex neurochemicals (such as glutamine), quantified as a cerebrospinal fluid (CSF)-corrected absolute concentration percent change from baseline, are associated with clinical remission of depression when active rTMS is used.

3 Study Design

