corpus callosum showing a continuous view of the anterior and posterior horns of the lateral ventricles will be chosen as a reference slice (Figure 2). The center of a single 4-cm³ voxel (2-x-2 cm in-plane resolution by 1 cm thick) of predominantly gray (prefrontal) matter is centered on the frontal interhemispheric fissure. The voxel's posterior margin is placed immediately anterior to the genu of the corpus callosum in an area corresponding to the pregenual AC cortex (Brodmann areas 24a, 24b, and 32). A second 8-cm³ voxel will be centered in white matter deep to the L-DLPFC, operationally defined as the gray matter of the superior frontal sulcus and large portions of the superior and middle frontal gyri, containing Brodmann's areas 9 and 46. A long echotime (TE=80 ms) standard PRESS sequence (TR=2000 ms, number of acquisitions=128, bandwidth 500 Hz, 4096 points) will be used to measure glutamate and glutamine as well as measure the other metabolites. A second 2D J-averaged MRS sequence (TE=35-195 ms in 16 steps of 10 ms each, TR=2000, number of acquisitions=128, bandwidth 500 Hz, 4096 points) will also be used to optimally measure glutamate in each voxel. All MRS data will be processed using LCModel, a well-accepted, unbiased program for determining metabolite concentrations. A quantitative analysis of brain metabolites will be performed with a focus on the target metabolites. Anatomical image data will be segmented into gray matter, white matter, and CSF using a semiautomated thresholding technique developed internally at MCR ([name], [name], [name]). This segmented anatomical data will be combined with the spectroscopic data to obtain tissue-volume-corrected metabolite concentrations per accepted methods. This generates "absolute" (versus relative to creatine) metabolite concentrations in "institutional units" specific to our scanner and technique. These concentrations will then be used in the statistical analysis. An accepted data standard for healthy controls in these particular voxel locations will be used in the comparison.

Figure 2 – Voxel Placement examples
Top = AC; Bottom = L-DLPFC

Phase II (Non-Randomized, Open-label):

Arm 1: Acute Treatment (Nonresponder Cohort)

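### Regional specificity (AC versus L-DLPFC) is a stated objective, but no planned analysis compares the two regions

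*Combined protocol and SAP*

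**What the plan says.** Section 2.2 gives the first spectroscopy objective as: "Define regional specificity [anterior cingulate (AC) and left dorsolateral prefrontal cortex (L-DLPFC)] of cerebral metabolites (i.e. glutamate and glutamine) in adolescent depression". The Study Summary carries it as objective 3a, at the Mayo site only.

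Section 7.2 attaches two hypotheses to the spectroscopy data.

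- Hypothesis 1: baseline glutamate "will be significantly higher in both AC and L-DLPFC in depressed adolescents", compared with healthy controls scanned previously.
- Hypothesis 2: remitters "will exhibit a greater decrease in glutamine, reported as a CSF-corrected absolute concentration percent change (baseline to endpoint) in AC and L-DLPFC", compared with non-remitters.

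On method, the section says "The hypotheses will be tested using t-tests", and that "analyses of covariance will be performed to control for potentially important covariates or confounders, such as age or gender". It also says "All statistical tests will be performed at the 0.05 significance level". The Study Summary repeats the same methods. On the controls, section 3.1 says "An accepted data standard for healthy controls in these particular voxel locations will be used in the comparison". It does not give their number, or say whether individual values or only summary norms are available.

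The Bonferroni rule in 7.2 is written for treatment groups, not for regions.

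**The concern.** Specificity is a statement about a difference between regions: the abnormality is larger in one than in the other. Neither hypothesis in 7.2 contains that difference, and region is not a factor in any named model. Confirming hypothesis 1, elevation in both regions, would give no evidence of specificity.

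The only inferential results bearing on objective 3a would then be two p-values, one per region. A significant result in one region beside a non-significant result in the other does not show that the regions differ. Two significant results do not show that they are alike. At stake is whether a secondary conclusion about where the abnormality lies could be drawn validly from these data.

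**Working it through.** **1. The plan's own figures.** Section 7.1 gives power only for the primary outcome, and those figures reproduce.

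| Comparison | 35 per group (stated) | 25 per group (stated) |
|---|---|---|
| 65% v 25% | 93.7% (94%) | 83.2% (83%) |
| 8.0 units, SD 10, normal approximation | 91.7% (91%) | 80.7% (80%) |
| Same, exact t | 91.0% | 79.1% |

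None of them concerns spectroscopy. The documents give no spectroscopy effect size, SD, control number or between-region correlation. Only the 50 Mayo patients come from the documents; the other inputs below are assumptions.

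**2. How often would exactly one region be significant when the true effects are equal?** Let p be the power in each region, from the noncentral t with noncentrality d√(50m/(50+m)) for 50 patients and m controls. Let ρ be the between-region correlation, z the standard normal quantile of p, and Φ₂ the bivariate normal distribution function. Then

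P(exactly one) = 2[p − Φ₂(z, z; ρ)], which is 2p(1−p) when ρ = 0.

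Example: for m = 50 and d = 0.5 the noncentrality is 0.5 × √25 = 2.5 and p = 0.697. At ρ = 0 this gives 2 × 0.697 × 0.303 = 42%. At ρ = 0.5 it is 29%, and at ρ = 0.7 it is 22%.

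| Per-region power | ρ = 0 | ρ = 0.5 | ρ = 0.7 |
|---|---|---|---|
| 0.05 (no effect) | 9.5% | 8.1% | 6.7% |
| 0.30 | 42% | 29% | 22% |
| 0.50 | 50% | 33% | 25% |
| 0.80 | 32% | 23% | 17% |
| 0.90 | 18% | 14% | 11% |
| 0.95 | 9.5% | 7.6% | 6.1% |

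For m = 20 to 50, d = 0.4 to 0.6 and ρ = 0.3 to 0.6, the formula gives 17% to 40% and simulation about 16% to 40%. At d = 0.8 with 50 v 50 the figure is only 3% to 4%.

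Hypothesis 2: averaging the 65% and 25% in 7.1 gives 45%, or roughly 22 remitters and 28 non-remitters. At d = 0.5 the result is 48%, 32% and 25% for ρ = 0, 0.5 and 0.7.

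**3. Separate tests can also miss a real difference.** With true effects of 1.2 and 0.7 SD and 50 v 50, exactly one region is significant in about 6% of runs, because both usually are. With 0.8 and 0.4 SD it is 46% to 49%.

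**4. A direct contrast.** Take each subject's AC value minus L-DLPFC value, both in SD units, and compare groups by a two-sample t-test. With equal effects (25 or 50 controls, d from 0 to 0.8, ρ from 0 to 0.7) it is positive in 4.7% to 5.4% of runs. The difference detectable with 80% power is

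(1.96 + 0.8416) × √(2(1−ρ)) × √(1/50 + 1/m).

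For m = 50 and ρ = 0.5 this is 2.8016 × 1 × 0.2 = 0.56 SD (0.79 at ρ = 0; 0.43 at ρ = 0.7). For m = 25 the three values are 0.97, 0.69 and 0.53 at ρ = 0, 0.5 and 0.7.

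**5. The scale matters.** Section 3.1 describes a 4 cm³ AC voxel of mainly gray matter and an 8 cm³ L-DLPFC voxel centered in white matter, so the SDs may differ. Suppose one SD is twice the other. On the raw scale, an equal standardized elevation d becomes a difference of d, with standard error √(5−4ρ) × √(1/50 + 1/m).

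- m = 20, d = 0.4, ρ = 0.3: 0.4/(1.949 × 0.2646) = 0.78, positive in about 12%.
- m = 50, d = 0.6, ρ = 0.6: 0.6/(1.612 × 0.2) = 1.86, positive in about 45%.

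**6. If only norms exist.** A paired test of patients' z-scores that treats the norms as fixed understates the standard error by a factor of √(1 + 50/m). For m = 20 the factor is 1.87, and the nominal 5% becomes P(|Z| > 1.96/1.87) = 29.5%. For m = 50 it is 1.41, giving 16.6%. Error in the norm SDs adds to this: simulation gives about 17% to 34% for 20 to 50 controls.

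**The case against.** A reader might infer that the plan will often report specificity where there is none. The documents do not support that. Nothing in 7.2 says that one significant and one non-significant region will be called specificity. The hypothesis is elevation in both regions, so a discordant pair is simply a failure to confirm it. Requiring both t-tests to be significant is a valid test of hypothesis 1. How often discordance arises rests on assumed values, and it is small when there is no effect or when power is very high. These points stand.

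The objective could also be read descriptively, as characterizing metabolites in two named regions. The wording allows this, but then the plan should say so and draw no inference about specificity. Separate testing by region is likewise a reading, since the plan says only that t-tests will be used. It is the natural one, given two named regions and control data by voxel location.

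The consequence is limited: this is a secondary, single-site aim in a pilot trial. Because the voxels differ in tissue, even a correct contrast would compare tissue types as well as regions. That limits its interpretation but does not supply the missing comparison.

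**Conclusion.** The gap is real and visible in the text: regional specificity is an objective, and no planned analysis compares the regions. The t-tests suit hypothesis 1 but cannot answer objective 3a.

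The risk is conditional on someone reading a one-region result as specificity. In that case, under the assumed inputs above, about 16% to 40% of studies would show the pattern with equal true effects, against under 10% with no effect or with per-region power of 0.95 or more. The point is worth correcting before analysis. It does not touch the primary outcome, safety or the trial's sample size.

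**What to change.** In 7.2, add for objective 3a a pre-specified group-by-region contrast that uses each subject's values in both voxels, reported with a confidence interval. Fix the scale in advance, for example standardized by region or log/percent, because the voxels differ in volume and tissue. Apply the same contrast to percent change in glutamine by remission status.

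If only summary control norms exist, the contrast must carry their sampling error, using the norm SDs, the control number and an assumed range of between-region correlation. A paired z-score test that treats the norms as fixed should not be used.

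If neither is possible, label objective 3a descriptive and draw no conclusion on specificity.

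The cost is a paragraph in the analysis plan and one contrast on data already planned. The downside is modest power: about 0.56 SD is the smallest difference detectable with 80% power at 50 v 50 and correlation 0.5 (control number and correlation assumed). The interval should therefore carry the interpretation, and a non-significant contrast should not be read as showing that the regions are alike.
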